8.2 Secondary Endpoints and Analysis

8.2.1 Hydroxyurea effect: We will compare the study outcomes between subjects with use and non-use of hydroxyurea using Chi-square, Mann-Whitney and mixed-effect linear models depending on the outcome scales and the format of the data (cross-sectional vs. longitudinal). In addition, we will also assess if the effects of hydroxyurea on the outcomes will be different between treatment arms by modeling interaction effects in pertinent statisticalmodels.

8.2.2 Microbiome analysis: This analysis will be performed by commercial labs. Our hypothesis suggests that specific microbes are predominant in leg ulcers of SCD patients. To identify these microbes, we will build on our previous characterization of the microbiome of HbSS legulcers compared to non-ulcers during the INSIGHTS study. The presence of such isolates may impede the healing process, worsening the condition and increasing healing time. To address this hypothesis, we will process and prepare samples for DNA extraction and sequencing from all study participants. Samples will then be sent off for sequencing using the MiSeq platform. We will first check for chimeras and, if any are identified, remove them from the sequence file. Then we will align and taxonomically classify our sequences using online microbial ecology tools like Qiime (or mothur) and a 16S (bacterial) and/or ITS (fungal) reference database to characterize the microbial communities present on the foot of HbSS patients with and without leg ulcers^{44,45}. Using the same bioinformatics tools, we will assign the amplicon sequences to operational taxonomic units using a percent similarity cutoff to further bin/group sequences. This step is important for the analysis employing diversity-based metrics to highlight community richness (Chao1) and microbial community structure (Theta Index) and membership (Jaccard Index). We will also infer phylogenetic relationships using the same tools (UniFrac) mentioned above. To visualize these relationships among microbial communities, we may also wish to conduct principal coordinates analyses (PCoA) to show similarities or differences between two environments (i.e. disease vs. healthy states). If we decide to sequence the fungal community present in the leg ulcers, we will follow the procedure described above with minor modifications, using CD-HIT for sequence clustering⁴⁶.

We will use the statistical software, R (http://www.r-project.org/), to represent visually the taxonomic classification of the sickle cell leg ulcer and diabetic foot ulcer data. UniFrac will require phylogenetic information generated in earlier steps of the analysis to compare both leg ulcer microbial community datasets⁴⁶. We will also employ Spearman's correlation to identify significant abundance relationships accounting for variation in each sample.

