The **primary objective** is to determine the safety of prolonged (10 weeks), twice a week application of topical sodium nitrite in patients with sickle cell disease and leg ulcers. We will do this by accomplishing the following specific aims: 1)To determine if topical sodium nitrite accelerates wound healing as defined by >25% improvement over placebo arm; 2) To determine if topical sodium nitrite decreases pain at the wound site>20% over placebo; 3) Secondary aims: a) To evaluate the effect of Hydroxyurea on leg ulcer's healing in combination with topical sodium nitrite or placebo; b) To assess changes in ulcer microbiome after application of sodium nitrite or placebo and how they may relate to healing; c) To evaluate the dermal composition and microvascular structure in the ulcer's biopsy of subjects enrolled on this study.

Significance

This phase II study is the next step in the drug development plan, as we move from a phase I dose-finding study to a more prolonged safety and tolerability study at a fixed dose, comparing to placebo.

The second aim is to develop data to indicate a preliminary signal for efficacy. We can be encouraged in this regard by the signs of an efficacy signal in the uncontrolled phase I study, comparing low dose to higher dose in patients with sickle cell disease and chronic legulcers.

The successful completion of this trial would allow us to define the effect size that would be utilized to plan for the next appropriately powered phase III study, a crucial step towards development of an effective therapy for this debilitating complication that affects patients with SCD worldwide.

From a practical standpoint, obtaining these data would be very helpful to attracting industry or venture capital or SBIR funding to ensure further drug development.

Research Strategy

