3.0 Specific Aims

Hypotheses:

- •Topical sodium nitrite cream, at 2% concentration, is safe and well tolerated when applied for an extended period of time (10 weeks) in patients with sickle cell disease and leg ulcers.
- •Topical sodium nitrite accelerates healing of skin ulcers and decreases ulcer relatedpain compared to placebo in patients with sickle cell disease and leg ulcers.

Specific Aims:

- To determine the safety and tolerability of prolonged (10 weeks), twice a week application of topical sodium nitrite in patients with sickle cell disease and leg ulcers
- To determine if topical sodium nitrite accelerates wound healing as defined by >25% improvement over placebo arm
- •To determine if topical sodium nitrite decreases pain at the wound site >20% over placebo

Secondary Objectives:

- To evaluate the effect of hydroxyurea on leg ulcer's healing in combination with topical sodium nitrite or placebo
- To assess changes in ulcer microbiome after application of sodium nitriteor placebo and how they may relate to rate of healing
- •To evaluate the dermal composition and microvascular structure in the ulcer's biopsy of subjects enrolled on this study.

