Rationale for the study of changes in microbiome. One of the most studied effects of NO is its bactericidal and general antimicrobial activity. NO exhibits nitrosative and oxidative action alone and after reacting with oxygen, such as peroxy-nitrite, RSNOs, and nitrogen dioxide⁴¹. These species affect microbial proteins, DNA, and metabolic enzymes, disrupting cellular walls and functions. NO acts on both planktonic bacteria and biofilm communities⁴². It is likely that a significant portion of the wound healing properties of NO are mediated through its bactericidal properties, through a reduction in biofilm and inflammation. We propose to examine changes in the microbiome.

Rationale for the sodium nitrite dose: The completed phase I, dose-escalating study identified the 2% concentration as the most effective for wound healing. Two of the three subjects in this cohort experienced complete closure, for a healing rate of 86%, higher than any of the other cream concentrations. The maximum sodium nitrite dose that will be administered to patients at this dose level is 55 mg per dose. This amount of sodium nitrite is 18% of the total sodium nitrite dose that is approved by the FDA for use in the emergency treatment of cyanide poisoning (i.e. 300 mg), and is predicted to produce a peak whole blood sodium nitrite concentration of approximately 29 µmol/L if given as an intravenous bolus or 5 µmol/L if infused over 15 minutes. These levels of systemic nitrite should be safe, as similar nitrite concentrations were observed and well tolerated in one of our healthy volunteer studies (05-H-0088). A median (range) nitrite peak concentration of 20 µmol/L and a steady state level of 8 (4 – 12) µmol/L were attained during the phase I study, significantly lower than what was previously reported to be safe. This indicates that sodium nitrite is minimally absorbed when applied topically, even on abraded skin. Methemoglobin reached 4.1% at its highest level in one subject, while did not change from baseline in any of the other 17 subjects. Mean arterial blood pressure did not change, while diastolic blood pressure decreased below a predetermined threshold of 50 mmHg in 2/3 subjects at this dose level. There was no correlation between nitrite and nitrate levels and changes in BP.

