- Apply 2 layer compression wrap to leg (depending on the condition of theulcer)
- Use of topical or systemic antimicrobials

All participants will be requested to complete the Brief Pain Inventory (BPI) prior to initiation of the therapeutic portion of the trial.

Baseline visit: The following tests will be performed:

- 1. Baseline labs, which include CBC, reticulocyte count, CRP, ESR, LDH, hepatic panel, basic metabolic panel, ferritin, Pro-B Natriuretic Peptide (BNP), urinalysis, urine microalbumin, uric acid, urine pregnancy test (female at reproductive age)
- 2. Research labs: Pax gene, and stored 5-10 cc blood samples
- 3. Saliva for DNA analysis
- 4. The surface area of ulcer(s) will be measured and photographed with defined lighting, distance, exposure and camera type
- 5. A pain assessment tool (VAS assessment)
- 6. Brief Pain Inventory (BPI), ASCQ-ME, PROMIS surveys, Beck Depression Inventory

Screening visit and baseline visits can be combined in one appointment.

After at least two weeks of "run in period", where the patient is treated with standard of care therapies only, the total ulcer surface will be measured and, if there isn't a reduction of>25%, the patient will be randomized to receive sodium nitrite cream or placebo.

A biopsy of the ulcer will be obtained in patients that consent during the run inperiod.

Week 1/Visit 3: First application of "study cream". After cleaning the wound, the wound will be measured by light photography and manually by wound nurse, a microbiome sample will be obtained, and the "study cream" will be applied to all the ulcerated surfaces. Vital signs will be obtained before application to establish baseline MAP and post-application at hours 1, 2, 3, 4, 5. If no significant decrease in MAP pressure from baseline is detected (clinically significant hypotension, or symptomatic dizziness, tachycardia, or hypoxia as per the judgment of the PI), the patient will be discharged and instructed to return for a second application two to three days later. Methemoglobin will be obtained one hour ± 30 min after creamapplication.

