Week 2-10/ Visits 4-22: The subjects will be seen twice a week for cream application, wound care and monitoring of side effects. The wound will be measured once a week manually by the wound care nurse and measured by photography after 10±2 applications. Blood pressure and vital signs will be measured upon arrival to outpatient unit and 30 minutes±10 minutes after the application of the study cream, unless clinically indicated. If the blood pressure is stable after cream application for all visit 4, 5, 6, post cream application blood pressure monitoring wound not be needed for future study visits. The wound will be cleaned and study cream will be applied.

Routine bloods will be drawn as clinically indicated. A research methemoglobin level will be obtained every other week.

A repeat pregnancy test will be performed at week 4 in women of reproductive age. Pain assessment: a VAS scale will be obtained with each application of the study cream. If there is more than one ulcer, individual VAS scale per ulcer will be obtained.

After the first three subjects have completed the first application of the study drug, if there are no significant side effects, especially significant changes in BP, patients will be offered the option of applying the second weekly dose of the cream at home, by themselves or by a home health nurse. We will dispense the exact amount of cream to be applied eachweek. This will reduce the number of visits to the wound care / hospital location to once a week.

End of study: Subjects will return the week after the last application to have the study cream removed and for end of study procedures. Blood pressure and vital signs will be measured with a pulse oximeter. The surface area of all ulcerated surfaces will be measured and photographed with defined lighting, distance, exposure, and camera. The wound doctor or nurse will remove the "study cream" and obtain a repeat microbiome sample. A VAS scale will be obtained to assess pain. If there is more than one ulcer, individual VAS scales will be obtained per ulcer. ASCQ-ME, PROMIS, BDI, and BPI surveys will be distributed to the patient. Study labs will be obtained (see Appendix 1). Patients who discontinue the study will still receive end of study procedures.

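### Section 8.2.2 specifies no analysis of the stated microbiome objective: the comparisons it names contain no treatment arm, no before/after change and no healing variable

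*Combined protocol and SAP*

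**What the plan says.** **Objective.** Section 3.0 lists, among the secondary objectives: "To assess changes in ulcer microbiome after application of sodium nitriteor placebo and how they may relate to rate of healing". The Precis carries the same aim: "To assess changes in ulcer microbiome after application of sodium nitrite or placebo and how they may relate to healing". The microbiome rationale in Section 5.2 argues that much of nitric oxide's healing effect may be antimicrobial and ends: "We propose to examine changes in the microbiome". It gives no contrast, measure or test.

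**Sampling.** Under Week 1/Visit 3 in Section 5.3, after wound cleaning and before the first application, "a microbiome sample will be obtained". At end of study, staff "obtain a repeat microbiome sample". The schedule table has one microbiome row, for the ulcer. It marks end of study and, for the pre-treatment sample, v2 in the run-in column rather than Visit 3.

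**Analysis.** Section 8.2.2 opens with a different question: "Our hypothesis suggests that specific microbes are predominant in leg ulcers of SCD patients". Sequences are classified "to characterize the microbial communities present on the foot of HbSS patients with and without leg ulcers". Chao1, Theta, Jaccard and UniFrac are named as measures. An optional principal coordinates plot is described as separating diseased from healthy environments. R will be used to "represent visually the taxonomic classification of the sickle cell leg ulcer and diabetic foot ulcer data", and UniFrac to compare the two ulcer datasets. The one correlation named is a Spearman analysis of abundances.

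**The concern.** A secondary objective needs an analysis that could answer it. This one concerns a treatment effect within a randomised trial, and a link between that effect and healing. Section 8.2.2 instead describes what lives in sickle cell ulcers and how that differs from other settings.

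Two things are at stake. First, someone following 8.2.2 as written would not produce the comparison that the randomised, paired swabs make possible. Second, if the analysis of change is devised later, the choices are wide: several diversity measures, many taxa, optional fungal sequencing, and either of two baseline visits. Without a pre-specified main comparison, a reader could not tell a planned result from a selected one.

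**Working it through.** The plan gives no sample size or precision figure for the microbiome, so there is none to reproduce. The main check is textual.

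**1. Objective against analysis**

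| Element of the objective (3.0, Precis) | In 8.2.2? |
|---|---|
| Nitrite or placebo | Neither the arms nor randomisation is mentioned |
| Change after application | No baseline-to-end-of-study comparison |
| Relation to healing | Impeded healing appears as motivation only; no ulcer-area or response variable enters an analysis |

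**2. Do other sections fill the gap?** The opening text of Section 8 and Sections 8.1.1 to 8.1.3 do not mention the microbiome. Section 8.2.1 compares hydroxyurea users with non-users and looks for an interaction with arm; that is not the effect of arm. Sections 8.1.2 and 8.1.3 each name an arm comparison and a test. Section 8.2.3 (biopsies) is openly labelled descriptive and exploratory. Section 8.2.2 has neither feature.

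**3. Can the named comparisons be made from the trial's swabs?** Section 4.2 requires at least one ulcer, so no group is enrolled without ulcers. Only ulcer swabs are scheduled, and no diabetic ulcers are sampled. All three comparisons need outside data.

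**4. What could the planned swabs detect?** Inputs: 20 completers per arm (Section 5.2), two-sided 0.05, 80% power, normal approximation, so the multiplier is 1.96 + 0.84 = 2.80.

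- Between-arm difference, 20 against 20 pairs: 2.80 × √(2/20) = 0.89 SD, about 0.9.
- Adjusted for the pre-treatment swab, pre/post correlation 0.5 (assumed): 0.89 × √(1 − 0.5²) = 0.77 SD, about 0.8 once a small t correction is allowed for.
- Half the nitrite arm closed and closed ulcers giving no swab (assumed), 10 against 20 pairs: 2.80 × √(1/10 + 1/20) = 1.08 SD unadjusted, about 1.1.
- Correlation of change with healing, Fisher z approximation: 40 subjects, tanh(2.80/√37) = 0.43; 20 in one arm, tanh(2.80/√17) = 0.59.

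Twenty pairs per arm assumes that every completer yields two usable swabs. The closure case matters because Section 7.2 stops study medication on healing, and Section 2.4 reports complete closure in two of three ulcers at 2% in phase 1. The documents do not say what is swabbed at end of study once an ulcer has closed. In the other direction, Section 5.3 gives subjects who discontinue the end-of-study procedures, so some non-completers could add pairs. Even all 25 randomised per arm would give 2.80 × √(2/25) = 0.79 SD unadjusted.

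**5. Baseline swab.** Section 5.3 says Visit 3; the schedule says v2. Standard wound care during run-in includes topical or systemic antimicrobials, so a v2 swab would fold part of the run-in effect into each subject's change.

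**The case against.** The strongest reply is that the intent is plain. Section 5.2 says that changes will be examined, the swabs are paired, and the measures named in 8.2.2 can all be applied to them. That stands as far as it goes. A reader might infer that the objective will never be analysed or that the swabs will go unused; the documents do not support that. They support only that no such analysis is specified.

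A reader might also take 8.2.2 as a formal test of ulcer against non-ulcer skin. That contrast belongs to the earlier INSIGHTS work on which the plan builds. The text here is a statement of purpose about patients with and without ulcers, and the ordination plot is optional. Nor is the diabetic comparison impossible: Section 2.1 describes a published sequenced series of 52 diabetic foot ulcers. The fault is that these comparisons do not address the objective.

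The Spearman sentence could be stretched to cover healing, but it names only abundances.

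On swab timing, it is tempting to say that a v2 baseline biases the treatment comparison. It does not. Run-in care is common to all subjects and precedes randomisation (Section 5.2), so the effect is on within-arm change, its correlation with healing, and precision. Wound care also continues throughout treatment, so a Visit 3 swab would not remove that influence.

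Finally, Section 5.2 says that the secondary endpoints were chosen to learn about the causes of poor healing. This partly explains the framing of 8.2.2, but the objective as worded still asks about change after treatment.

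**Conclusion.** The point holds in this form: Section 8.2.2 specifies no analysis of the stated microbiome objective, and the comparisons it does name answer another question and need data from outside the trial. This is more than missing detail.

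Its weight is moderate. No safety, ulcer-healing or pain conclusion depends on it, and a properly specified analysis would still be exploratory. It could detect only large between-arm differences: about 0.9 SD with 20 complete pairs per arm, about 0.8 SD after baseline adjustment (correlation 0.5 assumed), and about 1.1 SD if closure left 10 against 20 pairs (assumed). None of these figures allows for multiple testing. The textual finding does not depend on them. The change should be made because the data are already being collected and the cost is small.

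**What to change.** Make the following the main analysis in 8.2.2, labelled exploratory:

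1. End-of-study Chao1 compared between arms, adjusted for the pre-treatment swab and hydroxyurea stratum; genus-level results under false-discovery-rate control.
2. Each subject's pre-to-post shift in Theta, Jaccard and UniFrac, compared between arms by a permutation test.
3. Spearman correlation of each subject's change with percent ulcer-area reduction, overall and by arm.

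Other methods could serve; the requirement is a paired, between-arm and healing-related analysis fixed in advance.

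Add the rules it needs:

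- **Several ulcers:** state which one is swabbed, or how swabs are combined.
- **Closed ulcers:** state what happens at end of study, for example swab the healed site, or report the number missing by arm with a sensitivity analysis. Leaving closed ulcers out conditions on a post-randomisation outcome and could drop the best healers from the healing correlation.
- **Baseline:** reconcile Section 5.3 (Visit 3) with the schedule (v2), so that change has one defined starting point.

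Keep the non-ulcer and diabetic comparisons as descriptive, stated to be against external data.

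Cost: analysis wording and one schedule reconciliation. The planned swab occasions and sequencing stay the same.

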8.2.3 Microvascular structure analysis

Analysis of skin biopsies will be mostly descriptive as an exploratory analysis aimed at understanding the pathophysiology of ulceration in this population and at building a tissue repository analysis.

9. Human Subjects Protection

9.1 Inclusion of Women and Minorities

Because sickle cell disease primarily affects African-Americans and Latinos or Hispanics, we expect that most, if not all, the patients will be from these ethnic groups. However, no one will be excluded based on ethnicity. Because sickle cell disease is autosomally inherited, we expect to recruit an equal number of males and females. Criteria for exclusion or withdrawal from the study are based on the presence of other disease processes that may interfere with the interpretation of our results or situations that may be harmful to the healthy subjects.

26

9.2 Inclusion of Children

As this is a pilot study of an un-licensed medication that has not yet been tested in adults, children under the age of 18 will be excluded from this study.

9.3 Evaluation of Benefits and Risks/Discomforts

The level of risk to the adult research participants is greater than minimal risk with a prospect of direct benefit. This assessment is in accordance with 45 CFR 46.102 (h)(i).

Risks:

A literature search was performed using PubMed back to 1965 with the following search words: nitrite, sodium nitrite, toxicity, methemoglobinemia, humans. Literature searches were also performed by [name], principal investigator updating through 2015, using the following search terms: nitrite, sodium nitrite, toxicity, poisoning, adverse effects, human.

Sodium Nitrite: Sodium nitrite has been used commercially as a food preservative, an anti-corrosive agent, a coloring agent, and an anti-angina agent, with additional uses inlaxatives, burn ointments, and liniments. Amyl nitrite and isobutyl alcohol have been inhaled or ingested as euphoric stimulants. Nitrite has also been found as a contaminant in well water. The literature searches generated case reports of nausea, vomiting, abdominal pain, dizziness, headache, flushing, cyanosis, tachypnea, dyspnea, hypotension, and death attributed to excess nitrite (high dose) exposure from these sources as a consequence of methemoglobinemia due to oxidation of heme-iron in oxyhemoglobin. If levels of methemoglobin rise above approximately 30% of total hemoglobin, a subject may appear cyanotic and experience dyspnea, due to the reduced oxygen carrying capacity of hemoglobin (methemoglobin cannot bind oxygen). Levels above 50% can cause seizures, hypotension, coma, and death.

Nitrite in the form of sodium nitrite for parenteral administration is currently available and accepted by the FDA for use in the emergency treatment of cyanide poisoning. Nitrite administration at this dosage causes methemoglobinemia, a desirable effect in the treatment of cyanide poisoning, as methemoglobin binds to cyanide, thus protecting cellular mitochondria. Sodium nitrite (4 mg/kg, approximately 300 mg) was infused intravenously over 10 minutes in eight healthy volunteer subjects⁴⁸. Methemoglobin levels in venous blood samples rose from 0.02% at baseline to 5.7% of total hemoglobin following infusion of sodium nitrite, with no subject experiencing adverse events.

Sodium nitrite cream in association with citric acid has been used as a topical agent for the therapy of chronic leg ulcers in non-SCD patients. In these human studies, no systemic adverse events were noted. This reflects the prompt production of NO when nitrite is mixed with citric acid. The phase I study of topical sodium nitrite cream without an acid that we just completed did not cause significant elevation of methemoglobin. An oral formulation of sodium nitrite did not cause elevation on metHb, but caused modest decreases in blood pressure.⁴⁹

Blood Drawing: Some patients may experience localized bruising at the site where blood is drawn. Routine blood drawing protocol will be followed to minimize this risk.

Skin Biopsy: There is a small risk of bleeding and infection at the site of biopsy. There is a small but real risk of increase in localized pain for a short period of time. Lastly, we do not know if patients that have a tendency to develop leg ulcers, may develop a chronic ulcer after a biopsy.

ASCQ-me, PROMIS, Beck Depression Inventory: There are no risks or discomforts from taking part in the ASCQ-me, PROMIS, and Beck Depression Inventory Surveys other than possibly getting tired from answering the questions.

PI: [name] Version 5 *Brief Pain Inventory*: There are no risks or discomforts associated to completing the Brief Pain Inventory other than possibly "test fatigue" -- getting tired of answering questions.

